4.1 Sample size of the study

Sample size estimation (by single group)

Statistical test efficacy was calculated with postoperative pathologic complete response rate (pCR) as the primary study endpoint. α 0.05, the test efficacy is 80%, the postoperative pathological complete response rate after conventional treatment is 15%, and the estimated postoperative pathological complete response rate in the test group is 35%. Considering the loss of 10% of cases, the calculated sample size of the access group is 35 cases.

4.2 subject investigated

The study subjects of this project were obtained from 35 patients with pMMR / MSS locally advanced rectal cancer initially diagnosed in Yunnan Cancer Hospital (the Third Affiliated Hospital of Kunming Medical University) from September 2022 to March 2024.

4.3 Enrollment criteria

1) Disease characteristics

- Histological confirmation of rectal adenocarcinoma;
- Immunohistochemistry confirmed pMMR or / and pCR or / and NGS as MSS;
- The tumor location is within 12cm from the anal margin;
- Local advanced rectal cancer (stage II-III, cT 3-4 and / or N +);
* Preoperative staging method: pelvic MRI / transrectal ultrasound.
- No signs of intestinal obstruction; or obstruction relieved after proximal colostomy surgery;
- Preoperative thoracic, abdominal, and pelvic CT excluded distant metastases.

2) Patient characteristics

- Age: from 18 years old to 75 years old;
- Activity status score: ECOG 0-1;
- Life expectancy: greater than 2 years;
- Hematology: $WBC > 350010^6/L$; $PLT > 100000 \times 10^6/L$; $Hb > 10g/dL$;
- Liver function: SGOT and SGPT were less than 1.5 times the normal value; bilirubin was less than 1.5 mg/dL;
- Renal function: creatinine was $< 1.8 \text{ mg/dL}$;

- Other: non-pregnant or lactating women; no other malignant disease (except non-melanoma or carcinoma of the cervix) within 5 years or concurrent; no mental illness that prevents informed consent; no other serious disease that leads to shortened survival.
- Patients or family members can understand the study protocol and are willing to participate in the study, and sign a written informed consent form;
- Patients had good compliance and volunteered for scheduled follow-up, treatment, laboratory tests, and other study procedures.

3) Previous treatment

- No previous rectal cancer surgery;
- No prior chemotherapy or radiotherapy;
- No previous biological treatment;
- Previous endocrine therapy: no restriction.

4.4 Exclusion criteria

- CRC of microsatellite instability (MSI-H or dMMR);
- Chronic hepatitis B or C (high-copy viral DNA) with a history of HIV infection or an active phase;
- AD;
- Other active clinical serious infections (> NCI-CTC version 3.0);
- Clinical stage I patients;
- There is already preoperative evidence of distant metastasis;
- Bad fluid mass, organ function decompensation;
- History of pelvic or abdominal radiotherapy;
- Multiple primary cancer;
- Patients with epileptic seizures (e. g., steroids or antiepileptic therapy);
- History of other malignancies within 5 years, except for cured cervical carcinoma in situ or basal cell carcinoma of the skin;
- Chronic inflammatory intestinal disease, intestinal obstruction;
- Drug abuse and medical, psychological, or social conditions may interfere with patient participation in research or influence the assessment of study outcomes;
- Known or suspected allergy to study drug or to any drug given related to this trial;
- Any unstable condition or conditions that may compromise patient safety and compliance;

4.5 Exit standard

- The subject withdrew his informed consent and requested his withdrawal;
- Poor compliance, not administered according to the study protocol;
- After enrollment from the study, the patient requests withdrawal from the investigator or fails to complete the study schedule for any reason;
- Other circumstances deemed necessary to conclude the study.

4.6 Termination of treatment

- Serious adverse events or serious adverse reactions (SAEs) during the study;
- Delay treatment for more than 4 weeks for any reason (meaning all drugs in the delayed regimen).

4.7 Evaluation of the study findings

1) Efficacy evaluation of chemoradiotherapy

- CR: Pelvic MR: complete regression of primary tumor or only fibrotic scar, MR no mesangial lymph node enlargement; ultrasound colonoscopy: complete regression of primary tumor or only erythematous tiny ulcer or scar, no cancer remaining on biopsy; digital rectal tumor disappeared and no stiffness or nodules of intestinal wall.
- PR: tumor volume reduced by more than 30%, no new lesions;
- PD: tumor volume increased more than 20%, or new lesions.
- SD: The tumor volume did not change significantly, the reduction degree did not reach PR, and the increase degree did not reach PD;

2) Evaluation of the degree of radical operation

- R0 microscopic pathology examination cut margin has no residual tumor cells;
- The R1 microscopic pathological examination of the resection margin showed residual tumor cells;
- Residual tumor cells were visible at the macroscopic lower margins of R2.

3) Tumor response assessment

It is recommended to evaluate postoperative pathological specimens according to the tumor pathological withdrawal grade (tumor regression grading, TRG) criteria (see Annex 2); if not, a complete pathological response must be reported.

4) Evaluation of local recurrence or metastasis

When clinical symptoms occur (anal pain, hematochezia, lower limb edema, etc.), progressive elevation of CEA, or suspicious signs in chest or abdominal imaging, further examination is needed to find local recurrence or disease metastasis progression. Regional recurrence mainly refers to tumor recurrence in the local area or near the adjacent organs; distant metastasis refers to tumor recurrence outside the above areas. Disease-free survival is the absence of tumor recurrence or the occurrence of new colorectal cancer by systematic evaluation.

Clinical diagnosis of recurrence and metastasis must meet at least one of the following:

- 1 Imaging suggested recurrence (ultrasound, CT, MRI, PET-CT)
- 2 Positive cytology biopsy (ascites, anastomotic recurrence, suspicious imaging findings)

The reported date of recurrence is the date when recurrence was detected using the diagnostic method described above. In case of recurrence, the investigator should specify the site of recurrence and the diagnostic method used. When definitive imaging evidence cannot be obtained, a positive result of cytology or biopsy should be obtained. Elevated CEA alone could not be used as evidence of local recurrence or metastasis of rectal cancer.

5) Calculation of the survival period

Local-regional recurrence-free survival was defined as the time interval from the onset of randomization to the appearance of a local recurrence event. Tumor evaluation (CT / MRI of the abdomen and pelvic cavity or ultrasound and chest CT) and CEA testing must be performed every 6 or 12 months after randomization, or when the patient shows signs of progression (i. e., clinically indicated).

Disease-free survival (DFS) is defined as the time interval from the start of randomization and the occurrence of the event in the next segment. Tumor evaluation (CT / MRI of the abdomen and pelvic cavity or ultrasound and chest CT) and CEA testing must be performed every 6 or 12 months after randomization, or when the patient shows signs of progression (i. e., clinically indicated). The suspected lesion detected by ultrasound must be confirmed by CT / MRI. All re-operations or further anticancer therapy should also be documented.

Based on the purpose of this study, events that identified patients were no longer in the disease-free condition were defined as follows:

- The patient showed signs of the original tumor recurrence;
- The patient showed signs of a new colorectal cancer;
- Death from any cause.

Note: recurrence of any original tumor or occurrence of new colorectal cancer should be determined by cytological or histological methods

Confirm. No supporting evidence of other specific test findings (such as radiography, histology / cytology) cannot be based on isolated events such as increased CEA or unexplained clinical deterioration of the disease. The date of relapse was defined as the date of final confirmation of the targeted findings. Patients will thereafter be followed up for survival as planned.

If a recurrence of a confirmed colorectal cancer or the occurrence of a new colorectal cancer occurs during the study treatment period, patients will be withdrawn from the study treatment for survival follow-up. If the recurrence of colorectal cancer or the occurrence of a new colorectal cancer occurs during the study treatment period, the patient may be treated further according to the guidance of the investigator.

All tested patients will be followed for at least 2 years. For a biopsy, a biopsy report should be provided. Overall survival was the time from randomization to death. When the patient survived, the time to the last follow-up was taken as the overall survival period.

6) Evaluation of the toxic and side effects of adjuvant therapy

Toxicity evaluation according to the CTC criteria (version 5.0)

Follow-up of patient safety should include during treatment and 30 days after the end of the last cycle. The reason for the delay or interruption should be recorded in the CRF table.

7) ECOG (Appendix)

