Effectiveness evaluation criteria	
Tumor evaluation was performed throughout the study and analyzed using the Solid Tumor Efficacy Evaluation (RECIST) criteria (version 1.1,2009). Radiological imaging (CT, MRI) scans were performed, and the clinical complete response rate (cCR), objective response rate (ORR), and tumor staging rate (mrTRG) were determined and calculated for all patients.

statistical method	
Statistical analysis was performed using SPSS23.0 or SAS software. For the PPS and FAS data, and safety indicators for the SS data. Most of the data presented in this study were descriptive. For continuous data, it is

expressed by mean and standard deviation and percentage of index index.

(1) Baseline demographic data and disease characteristics:

Characteristics of the observed patients were summarized by descriptive statistics, including age, sex, clinical stage, and ECOG scores, etc.

(2) Analysis method of the primary endpoint:

After the completion of the whole neoadjuvant treatment, two doctors in the pathology department jointly evaluated the pathological complete response rate (pCR).

(3) Secondary endpoints analysis method:

A. After the end of the whole neoadjuvant treatment, two doctors from the pathology department jointly evaluated the tumor withdrawal grade (TRG), and the pathological decline rate.

B. The imaging results were evaluated by RECIST 1.1 standard to calculate the objective response rate (ORR) and tumor descent rate (mr TRG);

C. Patient quality of life (QoL) was evaluated using the Chinese version of the Cancer Patient Quality of Life Scale [EORTC QLQ-C30] (V3.0);

D. Safety indicators: The evaluation is based on the SS set, using NCI-CTC AE v5.0 criteria, listing the incidence of adverse events and serious adverse events, their clinical presentation characteristics, severity, occurrence time, duration, treatment method, and prognosis.

E. The rate of tumor descent, the rate of anal preservation, incidence of surgical complications, incidence of adverse events and incidence of serious adverse events were all expressed in percentage.

F. Survival analysis was performed by Kaplan-Meier to estimate the 2-year overall survival (OS) and disease-free survival (DFS);

Flow chart of the clinical trial

Flow-chart description of the clinical trial

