3.4 The Watch Wait policy

A "watchful wait" strategy (non-radical surgery) for patients whose tumor withdrawal achieved clinical complete remission (cCR) (watch-and-wait policy). Specific strategies include: digital rectal examination, tumor markers every 1 to 2 months for 2 years, thoracic, abdominal and pelvic CT, pelvic MRI, endorectal ultrasound, colonoscopy and biopsy, and even PET-CT every 3 months.

3.5 therapeutic review

1 Effectiveness: objective efficacy evaluation according to RECIST1.1 standard evaluation, divided into CR, PR, SD and PD (see 4.7 for details);

After the end of induction therapy (available), after the completion of concurrent chemoradiotherapy (available), after the end of consolidation therapy / before surgery (required) can be evaluated after neoadjuvant treatment, according to the following conditions:

- 1) The patient evaluation is CR: if anal preservation surgery is feasible, direct surgical resection; if anal preservation is impossible, after full communication and informed consent, wait for observation (wait and watch);
- 2) Patients were evaluated as PR or SD, with direct surgical resection;
- 3) The patient was evaluated as PD, but there was still possible R0 resection in preoperative evaluation, and surgical resection was performed;
- 4) If the patient is evaluated as PD and cannot be removed by R0, the replacement treatment plan should be discussed according to MDT;
- 5) If distant metastases during neoadjuvant therapy are treated in accordance with the guidelines for diagnosis and treatment of metastatic colorectal cancer.

* After completion of neoadjuvant therapy, patients must receive efficacy evaluation of the same means in the same center.

2 Surgical resection rate: R0, R1, R2 (R0 no residual tumor; R1 microscopic tumor residue; R2 gross tumor residue);

3 Safety: Observation and graded according to NCI CTC AE 5.0 toxicity criteria. Tumor markers, blood routine, blood biochemistry, and liver and kidney function were checked every 2 weeks. In the course of treatment, the occurrence of adverse reactions should be closely monitored, including edema, gastrointestinal reaction, leukopenia, anemia, hand and foot syndrome, rash, muscle spasm, diarrhea, etc., and the time,

degree, treatment methods and treatment results of adverse reactions should be recorded.

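### Section 4.7 applies RECIST's 30% and 20% limits to tumour volume, whereas the RECIST 1.1 rules named for response and ORR apply them to diameters

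*Combined protocol and SAP*

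**What the plan says.** The protocol summary names RECIST 1.1 twice. Under effectiveness evaluation, tumour assessments are to be "analyzed using the Solid Tumor Efficacy Evaluation (RECIST) criteria (version 1.1,2009"). Under item B of the secondary-endpoint methods, imaging is "evaluated by RECIST 1.1 standard to calculate the objective response rate (ORR").

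Section 3.5 calls for "objective efficacy evaluation according to RECIST1.1 standard evaluation, divided into CR, PR, SD and PD (see 4.7 for details"). Section 4.7, item 1, then grades size change in three lines:

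- Partial response is given as "PR: tumor volume reduced by more than 30%, no new lesions", which sets the 30% limit on volume.
- Progression is given as "PD: tumor volume increased more than 20%, or new lesions", which sets the 20% limit on volume as well.
- Stable disease lies between those two limits and is again framed in volume, with no mention of diameters.

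Attachment 3 (RECIST 1.1), Section 2.3.1, is different. PR is a fall of at least 30% from baseline in the summed target-lesion diameters. PD is a rise of at least 20% over the smallest sum on study, with a 5 mm absolute minimum, or any new lesion. Attachment 3, Section 2.3.4, equates a 20% increase in diameter with a 73% increase in volume.

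**The concern.** Section 4.7 keeps RECIST's percentages but changes the quantity they apply to. It also leaves out the smallest-sum reference for progression and the 5 mm minimum. Because Section 3.5 points to 4.7 for the detail, an assessor who follows the protocol reaches the volume rule before the diameter rule, and nothing says that Attachment 3 overrides it.

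Volume generally changes by a larger percentage than diameter, so a 30% fall in volume is usually an easier target than a 30% fall in diameter. Some patients who are stable under RECIST 1.1 could be counted as partial responders, and the reported ORR would not be the RECIST 1.1 ORR that the summary promises. In a single-arm study ORR can be read only against other studies, so it needs to be measured by the named definition. Two unreconciled rules also leave room to choose between them after the data are seen.

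The CR line of 4.7 is not part of this point.

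**Working it through.** **Inputs.** Section 4.7(1): PR at a volume fall above 30%; PD at a volume rise above 20%. Attachment 3, 2.3.1: PR at a diameter-sum fall of at least 30%; PD at a rise of at least 20% and at least 5 mm. Attachment 3, 2.3.4: a 20% diameter rise corresponds to a 73% volume rise. Section 4.1: 35 patients.

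**Step 1: reproduce the plan's own conversion.** With equal change in three dimensions, volume scales as the cube of diameter: 1.2³ − 1 = 72.8%, which rounds to the stated 73%. On the same basis a 30% diameter fall is a volume fall of 1 − 0.7³ = 65.7%. Volume limits equivalent to RECIST 1.1 would therefore be about 66% for PR and 73% for PD, not 30% and 20%.

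**Step 2: convert the 4.7 limits to diameter.** The documents do not say how tumours change shape, so let *k* be the number of dimensions that change equally, the measured one included.

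- Diameter fall at which 4.7 calls PR: 1 − 0.7^(1/k)
- Diameter rise at which 4.7 calls PD: 1.2^(1/k) − 1

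| Dimensions changing (k) | PR under 4.7 | PR under Attachment 3 | PD under 4.7 | PD under Attachment 3 |
|---|---|---|---|---|
| 3 | 11.2% | 30% | 6.3% | 20% and 5 mm |
| 2 | 16.3% | 30% | 9.5% | 20% and 5 mm |
| 1 | 30.0% | 30% | 20.0% | 20% and 5 mm |

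With k = 3, a tumour whose diameter falls by between 11.2% and 30% is PR under 4.7 and SD under Attachment 3. With k = 1 the PR gap vanishes.

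**Step 3: the missing 5 mm minimum.** The 4.7 progression limit corresponds to less than 5 mm of growth when the smallest sum is below 5 mm divided by the limit:

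- k = 3: 5 / 0.0627 = 79.8 mm
- k = 2: 5 / 0.0954 = 52.4 mm
- k = 1: 5 / 0.2000 = 25.0 mm

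So for small tumours a PD gap remains even when only one dimension changes.

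**Step 4: effect on ORR.** Each reclassified patient moves ORR by 1/35 = 2.9 percentage points if all 35 are evaluable. The documents give no distribution of tumour shrinkage, so the number reclassified cannot be calculated. It may be small: Section 1.2 reports an ORR of 100% in 12 MSS patients on a similar regimen, with the response criteria not stated. Near that ceiling, a looser PR limit has little to add.

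**Step 5: effect on treatment.** Section 3.5 states "Patients were evaluated as PR or SD, with direct surgical resection", and it also sends PD to surgery where R0 resection is still thought possible. Moving a patient between PR and SD changes nothing. A wrong PD label matters only where R0 resection is also judged impossible.

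**The case against.** The strongest reply is that the word for volume is a translation slip for size. The English is visibly machine-translated, no section describes volumetric measurement, and 4.7 keeps RECIST's pair of percentages, with an SD line that closely tracks the one in Attachment 3. On that reading 4.7 is shorthand for Attachment 3 rather than a rival rule, and the summary separately tells the analyst to calculate ORR by RECIST 1.1. This is plausible and cannot be settled from the documents. It lowers the chance that anyone would apply a volume rule, but it does not remove the contradiction. All three size-graded lines say volume, Attachment 3 itself distinguishes volume from diameter, and Section 3.5 makes 4.7 the place to look. Even if size was meant, 4.7 would still lack the diameter sum, the smallest-sum reference and the 5 mm condition.

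Two narrower objections stand in part. First, the 73% equivalence assumes equal change in all dimensions and appears in guidance on non-target disease, so the two scales can coincide in the one-dimensional case; the working shows that case. Second, the 5 mm clause in Attachment 3 is garbled and could be read as an alternative to the 20% rise. Its wording as a requirement favours the joint reading, but the millimetre figures in Step 3 depend on it. They are a side point on PD and do not affect the PR result.

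The objection that the impact is small is correct and is reflected in the grading.

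**Conclusion.** The concern holds, as a minor one. As worded, 4.7 contradicts the RECIST 1.1 rules that the plan names, and nothing in the protocol resolves the conflict. Confidence in the contradiction is high. Whether it would change any result is unknown.

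If 4.7 is applied literally, the diameter fall needed for PR lies between 11.2% and 30%, depending on how many dimensions change, against 30% under RECIST 1.1. Any effect through PR would raise ORR. Progression could be called too readily, but because 4.7 names no reference point the net direction for PD is not fixed, and PD is probably rare here.

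The reach is confined to ORR, a secondary endpoint with no threshold or decision rule, in a study whose summary says "Most of the data presented in this study were descriptive". The primary endpoint, the sample size of 35 and nearly all treatment decisions are unaffected.

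**What to change.** In Section 4.7(1), replace the three size-graded lines with the Attachment 3 rules:

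- **PR:** the sum of target-lesion diameters is down by at least 30% from baseline.
- **PD:** the sum is up by at least 20% from the smallest sum on study, with an absolute increase of at least 5 mm, or there is a new lesion.
- **SD:** neither of these.

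State that ORR is the proportion with RECIST 1.1 CR or PR as defined in Attachment 3, and add the cross-reference. As an optional clarification, label the existing 4.7 definition based on MRI, endoscopy, biopsy and digital examination as clinical complete response, the status used for watch-and-wait in Sections 3.4 and 3.5.

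The cost is a wording change and one cross-reference, with no added visits, scans or patients. ORR may come out slightly less favourable than under the volume rule.

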The prognosis of rectal cancer is worse than colon cancer, one of the important reasons is the high local recurrence rate after rectal cancer. Surgical resection is the main treatment for rectal cancer. Due to the complex pelvic structure and small surgical space, local advanced rectal cancer (Locally Advanced Rectal Cancer, LARC) patients with complete surgical resection is difficult, low anal rate, local recurrence rate and high complications, including high postoperative recurrence rate is the most noteworthy cause of poor prognosis of LARC, its radical postoperative local recurrence rate of 5% -15%, distant metastasis rate of 30% -40%, is one of the main factors in patients. However, with the proposal and development of the concept of multidisciplinary comprehensive therapy (MDT), the perioperative neoadjuvant radiotherapy and chemotherapy have gradually received attention in the overall treatment of LARC. Studies have reported that total rectal series resection after neoadjuvant chemoradiotherapy for LARC reduced the local recurrence rate from 25% – 40% to 6%^[3-4].

According to the 2021 CSCO guidelines for the diagnosis and treatment of colorectal cancer: recommended for T3 / T4 or N + patients ± interval chemotherapy (reevaluation) + rectal cancer radical resection plus adjuvant chemotherapy (class 1A evidence)^[5]. The National Comprehensive Cancer Network (National Comprehensive Cancer Network, NCCN) guidelines recommend "preoperative concurrent chemoradiotherapy + radical surgical ± adjuvant chemotherapy" as the standard treatment regimen for locally advanced rectal cancer (stages II, III), and recommend 6 months of perioperative treatment^[6]. This treatment regimen

reduced the 5-year local recurrence rate of rectal cancer to 5% -10%, and the local control effect was significantly improved^[7]. In the past decade, its mortality reduction has slowed due to its higher rate of distant metastasis (29% -39%)^[8]. In addition, there are some locally advanced rectal cancer patients, even before the preoperative synchronous radiotherapy and chemotherapy, but still can not guarantee the tumor radical resection^[9-10].

1.2 significance of studying

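### The DFS event list has no place for a tumour that is never cleared, so, read literally in all enrolled patients, it can only push the 2-year DFS rate upward

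*Combined protocol and SAP*

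**What the plan says.** Section 4.7 5) sets the time origin: "Disease-free survival (DFS) is defined as the time interval from the start of randomization and the occurrence of the event in the next segment". Under the words "events that identified patients were no longer in the disease-free condition were defined as follows" it then gives three events and no others: "The patient showed signs of the original tumor recurrence"; "The patient showed signs of a new colorectal cancer"; "Death from any cause". Section 4.7 4) describes DFS in the same terms, without progression or incomplete resection. It also treats distant metastasis as recurrence outside the local area.

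Section 3.10 assigns secondary efficacy to the ITT population, which it defines by randomization to one of two arms. The Protocol summary plans a Kaplan-Meier estimate of the 2-year rate.

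The plan also foresees patients whose tumour is not cleared. Section 3.5, item 4, reads: "If the patient is evaluated as PD and cannot be removed by R0, the replacement treatment plan should be discussed according to MDT". Sections 3.5 and 4.7 2) define R2 resection, the latter as "Residual tumor cells were visible at the macroscopic lower margins of R2". The background in section 1.1 says that preoperative chemoradiotherapy in some patients "but still can not guarantee the tumor radical resection".

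**The concern.** A recurrence list works when every patient is disease-free at time zero, as after a complete resection. In this trial everyone has a tumour at enrolment and some may keep it. A tumour that never disappeared cannot, in ordinary usage, recur. The gravest local failures then have no event to trigger.

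The 2-year DFS rate is a listed secondary endpoint and feeds the final conclusion in the section 5 schedule. With no control arm, it can only be read against rates from elsewhere. A definition that leaves out local treatment failure makes that comparison unsafe.

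**Working it through.** **Denominator.** The only design figure that can be recomputed is N = 35, from section 4.1: pCR 15% against 35%, alpha 0.05, power 80%, 10% loss. With the one-sample normal approximation and two-sided alpha (the sidedness is not stated):

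n = [(1.960·√(0.15·0.85) + 0.842·√(0.35·0.65)) / 0.20]² = 30.3, so 31; 31/0.9 = 34.4, so 35.

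The plan's figure is reproduced. It rests on pCR alone, so the DFS definition does not touch it. The plan states no DFS rate.

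**Which outcomes trigger an event.**

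| Outcome | Where foreseen | DFS event as written? |
|---|---|---|
| Local PD, not R0-resectable | 3.5, item 4 | No |
| R2 resection | 3.5; 4.7 2) | No |
| R1 resection | 3.5; 4.7 2) | No; handling not stated |
| Distant metastasis | 3.5, item 5 | Probably, through 4.7 4) |
| Residual tumour never resected, other than unresectable PD or metastatic disease | No explicit pathway | No; handling not stated |
| Death | 4.7 5) | Yes |

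**Size of the bias.** Let k be the number of never-cleared patients among N = 35, and a the share of them alive without a listed event at 2 years. If nobody is censored before 24 months, the Kaplan-Meier estimate is a simple proportion, and

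DFS (list as written) − DFS (failure to clear counted as an event) = k·a/35.

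One such survivor adds 1/35 = 2.9 points. The documents give neither k nor a, so the table shows a range in percentage points:

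| k | a = 0 | a = 0.5 | a = 1 |
|---|---|---|---|
| 0 | 0 | 0 | 0 |
| 1 | 0 | 1.4 | 2.9 |
| 2 | 0 | 2.9 | 5.7 |
| 3 | 0 | 4.3 | 8.6 |
| 4 | 0 | 5.7 | 11.4 |
| 5 | 0 | 7.1 | 14.3 |

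The difference is never negative.

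**What an unstated rule can do.** Assume k = 3, all three alive at 2 years without a listed event, and 24 of the other 32 patients event-free.

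- List applied literally: (24 + 3)/35 = 77.1%.
- The three censored before any other event: 24/32 = 75.0%.
- The three counted as events: 24/35 = 68.6%.

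The same data give results 8.6 points apart, and the plan does not say which applies.

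**The case against.** The strongest reply is that the plan is silent rather than wrong. The sentence that introduces the event list presupposes that patients had reached a disease-free state. No text says that a never-cleared patient is to be scored as a success; an analyst might censor, exclude or count that patient. This stands in part. A reader might infer that the plan rules such patients disease-free until death, but the documents support only that the list, applied literally, has that effect. Even then, a patient who develops metastases is probably captured through 4.7 4). Section 3.7, however, collects only survival status after progression, so a later metastasis may go unrecorded. Censoring would not cure the problem, as the illustration shows.

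The start before treatment is also an inference, because the stated origin does not exist. If DFS ran from surgery in cleared patients only, most of the problem would vanish. But no text restricts DFS in that way, and section 3.10 points to all enrolled patients.

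A reader might further infer that the protocol plans for residual tumour left unoperated as a pathway of its own. It does not: section 3.5 sends PR and SD to resection and reserves observation for CR. Such patients could arise only by leaving the schedule (section 4.5), and the plan does not say how DFS treats them.

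Finally, the frequency is unknown. The remark in section 1.1 concerns chemoradiotherapy without immunotherapy and gives no figure. One study cited in section 1.2 reports 100% R0 resection on an immunotherapy combination, but among only 12 MSS patients, all of whom had been operated on. Neither source fixes k.

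**Conclusion.** The concern holds as a gap in the definition whose possible error runs in one direction. The event list does not fit a population that starts with tumour in place, and two failures that section 3.5 foresees, unresectable local progression and R2 resection, are not events. Read literally, the 2-year DFS rate is overstated by k·a/35: nothing if there are no such patients or none is alive without a listed event at 2 years, and 2.9 points for each one who is.

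A reader might conclude that the rate will be overstated by at least 2.9 points. The documents do not support a lower bound above zero. The result assumes a start at enrolment or first dose, all 35 enrolled patients as the denominator, and no early censoring. DFS is secondary in an exploratory, mainly descriptive study, so the pCR analysis and the sample size are not affected.

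**What to change.** In section 4.7 5):

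- Replace randomization with enrolment or first dose as the start, and correct the population wording in section 3.10 to match.
- Add as events: progression that makes the tumour not R0-resectable, dated at that evaluation; R2 resection, dated at surgery; and distant metastasis at any time after the start.
- State how R1 resection and residual tumour that is never resected are handled. Do not backdate the latter to an evaluation made before it was known that no resection would follow.
- Exempt the added events from the note that requires cytological or histological confirmation, since they are dated by evaluation or surgery.
- Label the endpoint event-free survival.

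An alternative is to restrict DFS to patients rendered disease-free (R0 resection or cCR), timed from that date, and to report event-free survival for all enrolled patients.

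The cost is wording in sections 4.7 and 3.10. Response category and resection status are already assessed, and the evaluation before surgery is already required. No treatment rule changes. The downside is that the reported 2-year rate may be less favourable.
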